# 5.3 RULES FOR DISCONTINUING SUBJECT PARTICIPATION

### 5.3.1 Criteria for premature termination of an individual's participation in study

All residents included in the protocol who no longer wish to participate will be removed from the study as soon as this request is made.

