### 2.1.3 Primary endpoint

Quantitative measurement of ingesta (caloric and protein intake), monthly between M-1 (before implementation of the "finger-food") and M6.

The assessment of nutritional intakes will be carried out on 3 consecutive days, by a dietician, for lunch and dinner, at a point in time between M-1 and M0 (i.e. before the implementation of the "eat-in" system), and then monthly.

This dietary assessment will be done by means of photos BEFORE/ AFTER the consumption of the meal, by the housekeepers. The photos will target the actual consumption of the meal compared to the proposed service. This tool is preferred to the food monitoring form, usually used in the seniors's residents, but which does not allow for a detailed analysis of the food consumed and the quantities per dish actually ingested by the residents.

Also, the environment of the meal will be photographed in order not to wrongly consider the possible food losses, notably food on the ground, as food contributions. The residents' faces will not be photographed.

Information on the taking of these photographs will be provided to the appropriate people in order to have an image quality that is conducive to analysis and to respect a certain homogeneity of distance in the taking of photographs and in the analysis that will result from them.

The same dietician will ensure the analysis of the photos and intakes to avoid bias.

The photos will be analyzed using a quantitative and qualitative approach:

Meal consumption: A global evaluation of the meal will be done according to whether the resident ate all of his meal, /4, half, /4 of his meal or nothing at all, while taking

into account the environment.

- Type of dish consumed (starter / main course: meat-fish-egg, vegetable-starch / dairy product / dessert).
- The caloric (in kilocalories) and protein (in grams) intakes of the meal trays will be calculated before distribution to the residents.
- The same calculations will be made after the meal has been consumed, taking into account the environment and what the resident has actually eaten. They will be compared to the amount of the proposed meal tray in order to take into account residents with a poor appetite for whom half portions are usually proposed.

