### 3.2 STUDY DIAGRAM

# 3.3 RANDOMIZATION

The randomization will be done via the Clinsight software by connecting to the website: https://nantes-lrsy.hugo-online.fr/CSOnline/.

The connection will be done thanks to a login, a password and a study number, delivered by a data-manager of the Research Promotion Department of the CHD of La Roche/Yon.

The following information must be filled in:

- First initial of the name
- First initial of the first name
- Date of birth
- Compliance with inclusion and non-inclusion criteria (yes/no)
- Collection of non-objection (yes/no).

The inclusion number will be assigned automatically during randomization. An e-mail confirmation will be sent to the person who performed the randomization and to all the persons concerned.

The randomization list will be carried out by a statistician from the Research Promotion Department of the CHD of La Roche/Yon.

A guide to the randomization procedure will be available online under Clinsight.

Randomization will be stratified by center (seniors's residents) and performed in a 1:1 ratio.

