### 5.3.2 Procedures in respect of early withdrawal of a subject from the study

The management of a resident who is prematurely discharged from the study will be identical to the usual management.

In the event that a resident wants to leave the study, he/she will be able to continue to benefit from the "eat-in" if he/she wishes.

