### Primary endpoint :

The evolution of caloric and protein intakes between inclusion and 6 months will be compared between the 2 groups by a Wilcoxon Mann-Whitney test.

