### 6.2.3 Expected level of statistical significance

The significance level is set at 5%.

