### 6.2.5 Consideration method for missing, unused or invalid data

The main criterion being the comparison of the evolution of the quantity of ingesta between the inclusion and the 6 months of follow-up, a missing value of these data will entail an imputation of this one by the worst value then, by the average of its group.

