### 6.2.7 Choice of subjects to be included in analysis

All residents included in the study will be analyzed.

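### The plan has a single exit with no agreed continued measurement, so a resident who leaves may keep eating finger-food yet enter the primary analysis with an imputed intake.

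*Combined protocol and SAP*

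**What the plan says.** Section 5.3.1 is the only rule for ending an individual's participation: residents "who no longer wish to participate will be removed from the study as soon as this request is made". Section 5.3.2 adds that a resident who leaves may stay on the study food: "he/she will be able to continue to benefit from the 'eat-in' if he/she wishes".

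Section 6.2.7 sets the analysis population: "All residents included in the study will be analyzed". For the primary criterion, section 6.2.5 says that "a missing value of these data will entail an imputation of this one by the worst value then, by the average of its group". Under section 6.2.1, the change in caloric and protein intake from inclusion to 6 months "will be compared between the 2 groups by a Wilcoxon Mann-Whitney test".

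Intake comes from before-and-after meal photographs over 3 consecutive days each month, not from the routine record. Section 2.1.3 says of the photographs: "This tool is preferred to the food monitoring form, usually used in the seniors's residents". Once a resident leaves, routine care therefore does not supply the primary measurement.

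The trial is open (section 3.1), and only the finger-food arm changes its lunch and dinner format (section 5.1, Step 2). In section 5.1, the text on communication to families anticipates reticence about eating with the fingers and aims to limit it.

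**The concern.** Read together, these sections allow a resident to ask to leave, go on eating finger-food in a participating residence, and still be counted in the primary comparison with an intake that nobody measured. The plan does not say that a resident may stop the assigned format and remain under measurement, nor that a resident who leaves may be asked to allow the monthly photographs to continue.

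At stake is the comparison of the randomised groups. In an open trial where one arm alone changes format, exits could plausibly be more frequent in that arm. Worst-value imputation would then pull that arm down, while group-mean imputation would give leavers the level of those who stayed and understate the variability. Residents who reject the format are also among those a pilot most needs to learn about: how many there are, why they stop, and what they then eat.

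**Working it through.** **Is there a figure to reproduce?** No. Section 6.2.2 states that no sample-size calculation was done, and no exit rate, SD or effect size is given.

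**Inputs from the plan.** About 60 eligible residents (section 4.1), allocation "performed in a 1:1 ratio" (section 3.3), hence 60/2 = 30 per arm; Wilcoxon Mann-Whitney test (section 6.2.1); 5% level (section 6.2.3).

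**Assumptions.** Two-sided test; normal change scores with SD 1; exits completely at random; 0, 3 or 6 exits per arm (0%, 10%, 20%). Section 6.2.5 does not define the worst value, so two readings are used: the lowest observed change within the resident's arm, and the lowest over both arms. It is also unclear how the worst value and the group average are to be combined, so each is run alone.

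**Step 1: size of the shift.** If k1 finger-food and k0 control residents leave, and the imputed value lies w SD below the mean, then

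shift = -(k1 - k0)/30 × w.

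In simulated samples of this size, w is about 2.0 within arm and about 2.3 over both arms.

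- 3 v 0: -(3/30) × 2.0 = -0.20; -(3/30) × 2.3 = -0.23
- 6 v 0: -(6/30) × 2.0 = -0.40; -(6/30) × 2.3 = -0.46
- 6 v 3: -(3/30) × 2.0 = -0.20; -(3/30) × 2.3 = -0.23

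**Step 2: rejection rate with no true effect.** The imputation itself was simulated and the planned test applied (20,000 trials per cell).

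| Exits, finger-food v control | Intake still measured | Worst value, both arms | Worst value, within arm | Group mean |
|---|---|---|---|---|
| 3 v 0 | 4.7% | 7.8% (shift -0.23) | 7.7% (-0.20) | 6.6% |
| 6 v 0 | 4.9% | 22.3% (-0.46) | 21.2% (-0.39) | 8.8% |
| 6 v 3 | 4.9% | 5.1% (-0.23) | 7.1% (-0.19) | 12.0% |
| 3 v 3 | 4.9% | 2.1% (0) | 2.9% (0) | 8.9% |
| 6 v 6 | 4.9% | 0.5% (0) | 3.9% (0) | 17.0% |

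The group-mean shift is about 0 throughout, but only because exits were taken to be random. Its excess rejection comes from treating identical filled-in values as real observations.

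**Step 3: a true benefit.** The worst-value shift runs against finger-food, so its main practical effect is to hide a benefit. With an assumed true benefit of 0.7 SD, power is about 73% with measured intake. Under worst-value imputation it falls to about 36-41% at 3 v 0, 5-16% at 6 v 0 and 14-32% at 6 v 3, according to the reading of worst value. Group-mean imputation gives about 75-80%. The two named imputations could therefore lead to opposite conclusions from the same trial.

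**The case against.** The strongest reply is that stopping on request is the resident's right. Section 11.3 guarantees withdrawal at any time, in a population that includes people unable to understand the study. A leaver's intake is not there for the taking; it can be recorded only if the resident or family does not object. That stands, and the fix must respect it.

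Four stronger readings are tempting, and the documents do not support them.

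- A reader might infer that refusing finger-food ends measurement. Section 5.3.1 covers only residents who ask to leave the study. One who stops the format without asking to leave is not removed, and section 5.1 relays advice that cutlery be left available. The plan is silent on this resident, which differs from a rule that excludes them.
- A reader might infer that every measurement stops. The text says removal from the study. That is a fair inference for the photographs, a study procedure, but the plan does not address routine file data or data already collected.
- A reader might take exits to fall in one arm only. Section 5.1 raises reticence in order to limit it and predicts no exits; control residents or families may also leave.
- A reader might treat a 0.2 SD shift as a pure shift in location and expect about 11% rejection. Imputing a few identical extreme values also widens the spread and creates ties, and the rank test then rejects in about 5-8% of trials at that shift.

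It is also fair to say that the group-mean inflation belongs to section 6.2.5 and would arise equally from death, hospitalisation or missed photographs. Pilot status is a weaker defence: section 6.2.2 says the purpose is to collect preliminary data, and imputed values are not data.

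**Conclusion.** The point holds as a gap in the plan: one exit, no distinction between stopping the format and declining data collection, and no offer of continued measurement, while the leaver remains in the primary analysis with an imputed value. It should be corrected, but it does not by itself invalidate the trial.

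Its size depends on exits that the documents do not quantify. With 3 v 0 the distortion is modest; with 6 v 0 it is serious; with equal exits of 3 or 6 per arm, worst-value imputation causes no bias and rejects below 5%, while group-mean imputation still rejects too often. These figures rest on 30 per arm, normal changes and random exits. If leavers differ systematically from those who stay, the group mean would be biased too. Unequal exits are plausible here, not established.

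**What to change.** In sections 5.3.1 and 5.3.2:

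1. State that stopping the assigned meal format is not withdrawal, and that scheduled measurement continues.
2. Ask any resident who leaves, or the family or guardian, whether the monthly photographs, weight and scales may continue.
3. End measurement only on refusal of data collection or on death.
4. Record the date, the reason and the meal format actually eaten.

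In section 6.2.7, add that observed values are analysed in the randomised arm, whatever format was eaten.

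The cost is a short amendment, for which section 11.2 already provides the route, one line on the information and non-objection form, and continued photographs in residences where staff already take them. No change to care is involved. Some residents will decline, so some data will stay missing, and the imputation rule in section 6.2.5 must be clarified separately.

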### 5.3.2 Procedures in respect of early withdrawal of a subject from the study

The management of a resident who is prematurely discharged from the study will be identical to the usual management.

In the event that a resident wants to leave the study, he/she will be able to continue to benefit from the "eat-in" if he/she wishes.

# 5.3.3 Criteria in respect of discontinuation of all or part of the study (excluding biostatistical considerations)

The end of the study is defined as the end of the participation of the last subject. Reasons for premature, definitive or temporary termination of the study may come from the decision of the sponsor or the coordinating investigators, for example for lack of inclusion.

# 6. DATA MANAGEMENT AND STATISTICS

### 6.1 STUDY DATA COLLECTION AND PROCESSING

### 6.1.1 Data collection

A Case Report Form (CRF/eCRF) will be allocated to each resident. All information required by the protocol will be recorded in the CRF/eCRF. It must include patient's identity, data required for compliance with the protocol, data necessary for statistical analysis, and any major deviations from the protocol.

The data collection will be done on a Clinsight database, developed by the data manager of the CHD Vendée promotion unit.

### 6.1.2 Data coding

By signing this protocol, the principal investigator and all the co-investigators undertake to keep the identities of the patients taking part in the study confidential.

The transmission of a person's data for research purposes will therefore only be possible if a coding system is applied; the presentation of the research results must exclude any direct or indirect identification.

A code will be set up for each resident. This code will be the only information that will appear on the observation book (CRF) and will allow the CRF to be linked to the resident after the fact.

The research supervisor will also code the resident data on any documents he/she may have in his/her possession (biology reports, etc.) that are attached to the CRF.

Only the first letter of the subject's name and the first letter of the subject's first name will be recorded, along with a coded number specific to the study indicating the center number and the order of inclusion of subjects.

Each investigating center will maintain a file of correspondence between the study code and the identity of the subjects at its own center. None of this direct or indirect identifying information will be available for study analysis and will be kept only at the center concerned.

### 6.1.3 Data processing

Clinical data collection shall be recorded on a database and creating input templates similar to the CRF in compliance with the protocol and applicable regulations.

The structure of the database and data input screens shall be approved by the trial sponsor.

# 6.2.1 Description of planned statistical methods, including planned intermediate analysis schedule

The description of quantitative variables will include the minimum, maximum, quartiles, mean and standard deviation. The description of qualitative variables will include the number and percentage of each modality.

### Primary endpoint :

The evolution of caloric and protein intakes between inclusion and 6 months will be compared between the 2 groups by a Wilcoxon Mann-Whitney test.

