### STEP 1 : M-1 - M0

This step includes resident selection, resident unopposed, and evaluation before randomization.

• Inclusion of residents

Once the regulatory authorizations have been obtained (CPP, CNIL), the residents of the CHD Vendée's seniors's residents will be selected from all the residents meeting the inclusion and non-inclusion criteria. Then each resident and/or family/guardian will be informed by the principal investigator of each seniors's residents and a note of information and non-objection will be given to them (Appendix 2).

Initial assessment

The project will evaluate with the residents involved in the project:

**Nutritional indicators:** Nutritional intake (qualitative measurement of ingesta), weight, BMI, biological indicators, MNA screening score

Associated comorbidities: Number of wounds and pressure sores, number of falls

Autonomy: Autonomy of feeding and physical or psychological autonomy

Behavior around the meal

Resident satisfaction / enjoyment of food

Hospitality/care workload of seniors's residents professionals

Significant events on dietary intake, MAP, NOD, laxatives and any hospitalization will be tracked during this period.

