### 5.2 STUDY SCHEDULE

Actions		Inclusion	M-1 to M0	M0 to M1	M1 to M2	M2 to M3	M3 to M4	M4 to M5	M5 to M6
Collection of non-opposition Size measurement		X							
Randomization			х						
Collection of consumption: nutritional intake*.			х	х	х	x	х	х	x
Nutritional Indicators**			x	x	Х	Х	х	x	х
Nutritional Indicators***			Х						х
Associated comorbidities ****			Х	Х	Х	Х	Х	Х	Х
Autonomy	Power supply (EBS)		Х			Х			Х
Autonomy	GIR		Х						Х
Eating behavior (Blandford scale)			Х			x			х
Resident satisfaction (VAS of faces)			Х	Х	Х	X	Х	Х	x
Impact on professionnals			Х	Х	Х	X	Х	Х	x
Significant events on food intake *****			Х	Х	Х	Х	Х	Х	Х

\*3 consecutive days, for lunch and dinner, at a time t between M-1 and M0, then monthly

\*\*Weight, BMI \*\*\* Biological indicators (albumin/ pre-albumine/ CRP), MNA screening score \*\*\*\* Number of pressure score and severity, number of falls, infectious complications: over the entire study period \*\*\*\*\* Medical and environmental events, drug consumption, hospitalization (number, reasons, duration)

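### The primary analysis plans a valid rank test but no between-arm difference with a confidence interval, and makes no adjustment for the baseline intake it already collects.

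*Combined protocol and SAP*

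**What the plan says.** The primary analysis in 6.2.1 reads: "The evolution of caloric and protein intakes between inclusion and 6 months will be compared between the 2 groups by a Wilcoxon Mann-Whitney test". Section 6.2.3 sets the 5% level. On summaries, 6.2.1 says: "The description of quantitative variables will include the minimum, maximum, quartiles, mean and standard deviation". It does not say that these are given by arm or for the change. For secondary endpoints it adds graphs and more Wilcoxon tests. No covariate, stratified test, model, effect estimate or confidence interval is named anywhere from 6.2.1 to 6.2.7.

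Other parts of the plan bear on this:
- Section 3.3: "Randomization will be stratified by center (seniors's residents) and performed in a 1:1 ratio". Home does not appear in the analysis.
- Section 5.2, on intake: "3 consecutive days, for lunch and dinner, at a time t between M-1 and M0, then monthly". A baseline value is therefore planned for each resident, and Step 1 of section 5.1 places that evaluation before randomisation.
- Section 6.2.5, on the main criterion: "a missing value of these data will entail an imputation of this one by the worst value then, by the average of its group".
- Section 6.2.7: "All residents included in the study will be analyzed".
- Section 6.2.2 states that no sample size calculation was made and that the pilot is to supply preliminary data. The expected results in the Summary look ahead to hypotheses and an impact study.

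**The concern.** A later study will need the likely difference in kcal and g, how uncertain it is, and the residual SD. A Wilcoxon p-value gives none of these. With about 60 residents expected (section 4.1) and no power target, a non-significant result is quite possible even if finger-food works. A bare p-value would then say very little.

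The second issue is efficiency. Baseline intake is measured anyway and is likely to predict M6 intake. The plan makes no adjustment for it beyond whatever is implied by *evolution*, a word that neither 6.2.1 nor 6.2.5 defines as absolute or relative change.

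**Working it through.** **No figure to reproduce.** Section 6.2.2 reports no calculation, and the figure of about 60 in 4.1 is a count of residents expected to be eligible. I take 30 per arm, a two-sided 5% level and complete data unless stated.

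**1. What a p-value leaves out.** The 95% CI half-width for a difference in mean change is 1.96 × √(2/30) = 0.51 SD of change. The difference detectable with 80% power is (1.96 + 0.842) × √(2/30) = 0.72 SD of change. For the Wilcoxon test under normality it is 0.72/√(3/π) = 0.74. At a true difference of 0.5 SD of change, Wilcoxon power is about 47%. A wide range of effects is compatible with either outcome of the test.

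**2. Adjusting for baseline.** Assume that *evolution* is M6 minus baseline, with SD 1 at both times and correlation ρ (not given in the documents).
- Variance of change: 2(1 − ρ).
- Variance of M6 given baseline: 1 − ρ².
- Ratio: (1 − ρ²)/[2(1 − ρ)] = (1 + ρ)/2.

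At ρ = 0.5 the ratio is 0.75, so a change-score analysis needs 60/0.75 = 80 residents to match an adjusted one with 60. At ρ = 0.9 it needs 60/0.95 = 63.

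**3. Simulation.** Set-up: 6 homes of 10, 1:1 within home, normal data, effect 0.5 SD of intake, no divergence between homes over time. The linear model is M6 intake on arm, baseline and home. Half-widths are in SD of intake.

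| Assumed ρ | (1+ρ)/2 | CI half-width, Hodges-Lehmann on change | CI half-width, linear model | Power, planned test | Power, linear model |
|---|---|---|---|---|---|
| 0.3 | 0.65 | 0.63 | 0.50 | 35% | 52% |
| 0.5 | 0.75 | 0.53 | 0.45 | 42% | 57% |
| 0.7 | 0.85 | 0.41 | 0.37 | 66% | 76% |
| 0.9 | 0.95 | 0.24 | 0.23 | 99% | 99% |

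Repeat runs gave 33–35, 42–47, 65–67 and 98.5–99% for the planned test, and 50–52, 57–60, 74–76 and 99% for the linear model. Of the gain, 15/13/6/0 points come from baseline, 2 to 3 points (0.5 at ρ = 0.9) from leaving ranks, and none from home.

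**4. Interaction with the missing-data rule.** Section 6.2.5 replaces missing values by the worst value. With 10% of M6 values (assumed) set to the worst observed value, power at ρ = 0.3/0.5/0.7/0.9 is:
- planned test: 26/34/48/90%;
- linear model: 32/36/41/52%;
- rank analysis of covariance on change (ranked baseline, home): 34/40/53/90%.

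Least squares on worst-value data therefore has less power than the planned test at ρ = 0.7 and above. Its mean estimate falls to 0.45 against a true 0.50. Fitted to observed values only, with 10% missing at random, the linear model has a mean estimate of 0.50 and half-widths of 0.53/0.48/0.40/0.24.

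**5. Home.** Stable differences between homes cancel in a change score. A Wilcoxon test stratified by home (van Elteren) changes power by −2 to +1 points when homes do not diverge. If they diverge with an assumed SD of 0.3, including home adds 3/4/4/2 points to the linear model.

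**The case against.** The best counter-argument is that the plan breaks no rule. The test is valid under randomisation, no power target is missed because none is set, and 6.2.2 asks only for preliminary data. If the summaries in 6.2.1 are given by arm for baseline, M6 and change, a later team could derive a crude difference, an approximate interval and the SD. This has weight and limits the harm. But 6.2.1 promises those summaries neither by arm nor for the change, and the derived difference would be unadjusted.

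A second argument is that adjustment is a preference resting on an unknown ρ, and that least squares can lose. That is partly right. The gain vanishes at ρ = 0.9. With heavy-tailed or skewed residuals at ρ = 0.7 the linear model has 80% and 76% power against 84% and 83% for the planned test. Rank analysis of covariance does not lose there (91% and 90%). This is a reason to keep a rank test, not to omit the estimate.

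A third is that a model on observed M6 values sits badly with 6.2.7, which analyses every included resident. This is met by keeping the rank test as the analysis of all included residents.

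Some stronger readings are tempting but unsupported:
- *The analysis is biased, or ignoring the stratification factor inflates type I error.* It does not. Simulated type I error of the planned test on complete or worst-value data is 4.4–5.7% without divergence between homes and 2.1–4.5% with it, so the test is if anything conservative.
- *Leaving out home is a serious defect.* Nothing in the documents suggests that homes diverge after baseline. Section 5.1 plans one production process for all sites, and 2.1.3 has one dietician reading all the photographs.
- *Baseline is certainly used only by subtraction.* This is the natural reading, but *evolution* is undefined. Either way, no baseline adjustment is planned.
- *The baseline timing is contradictory.* Sections 2.1.3 and 5.2 do not conflict with Step 1 of 5.1; they say less. The wording there, and the imputation rule itself, are separate matters.

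**Conclusion.** The point holds as a gap in reporting and a loss of precision. The missing effect estimate and interval follow directly from 6.2.1 to 6.2.7 and depend on no assumption. The text between 6.1.3 and 6.2.1 was not available to check.

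The size of the efficiency loss does depend on assumptions: absolute change, 60 residents, normal complete data, a 0.5 SD effect and ρ. On these, adjustment raises power by about 17, 15, 10 and 0 points at ρ = 0.3, 0.5, 0.7 and 0.9 (52−35, 57−42, 76−66, 99−99). Home is a minor point, included only because randomisation is stratified by it. The change should be made, but the planned test is not invalid without it.

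**What to change.** In 6.2.1, for calories and for protein:

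1. Report the between-arm difference at M6 (kcal and g, lunch plus dinner, the meals measured) with a 95% CI and the residual SD. Take it from a linear model of M6 intake on arm, baseline intake and home, fitted to observed M6 values.
2. Keep the rank test, if wished, as the test of all included residents under 6.2.7, and report a Hodges-Lehmann shift with 95% CI beside it. Define *evolution*, so that the shift has a clear unit. If the test is to use baseline too, use rank analysis of covariance on change with ranked baseline and home. A van Elteren test is optional and not part of the minimum.
3. State that the least-squares model is not fitted to the worst-value data of 6.2.5.

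The cost is SAP wording and a little analysis, with no extra data or residents. The model uses about 6 more degrees of freedom (1 for baseline, 5 for home, leaving 58 − 6 = 52). Little is gained if ρ is high. The observed-data estimate assumes that missingness is explained by arm, baseline and home. In an assumed case where low intake itself drives missingness (10% in controls, 6% with finger-food), it gives 0.47–0.49 against a true 0.50. The worst-value rank analysis should therefore remain as a check.

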	- Impacts on serniors's resident professionals					
	- Significant events on food intake					
	Inclusion criteria :					
	- Residents institutionalized in seniors's resident for 3 months					
	at least Decidents in dischility to food single handedly because of					
	
 
Residents in disability to feed single-handedly because of cognitive and/or physical disorders
 
					
	- Having at least use of a hand					
	- Do not opposing the participation in the study or information					
	and not opposition of the family / close to confidence / legal					
Criteria	guardian in case of resident in incapacity to understand					
	(senility, insanity)					
	Exclusion criteria :					
	- Confined to bed					
	
 
Specific diets (without residue, allergen,)
 
Enteral nutrition
 
					
	
 
Absence motricity of 2 hands
 
					
	Quantitative measurement of ingesta (caloric and protein intake),					
Primary endpoint	monthly between M-1 (before implementation of the "finger-food")					
	and M6.					
	Nutritional indicators:					
	Weight curve BMI					
	Biological indicators: Albumin / Pre-albumin, CRP					
	MNA Score Screening					
	Associated Comorbidities:					
	Number of wounds and pressure sores					
	Number of falls					
Secondary endpoint(s)	Autonomy					
	Autonomy : Power supply autonomy: EBS					
	Physical or psychological autonomy: GIR					
	Behavior around the meal:					
	- Assessment of eating disorders: Blandford scale					
	Resident satisfaction / enjoyment of food: VAS					
	Hospitality/care load of seniors's resident professionals					

Expected results	
 
This study will evaluate each of the defined evaluation criteria, analyze them in order to measure their impact on the following criteria: 
 
Maintain and/or improve the nutritional status of residents
 
Improvement of autonomy, behavior, quality of life
 
Reduction of associated comorbidities
 
 
 
Then to think about other projects, by formalising hypotheses, with an impact study.
 

------------------	--

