#### 2.2.2 Secondary endpoints

All endpoints will be compared between the no "finger-food" period (M-1 - M0) and the resident follow-up period (M0 to M6) depending on the randomization arm.

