#### Secondary endpoints :

The evolution of all the parameters collected throughout the monitoring will be described graphically.

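### The primary rank test of the inclusion-to-M6 change uses neither baseline intake as a covariate nor the stratifying home, and the imputation rule in 6.2.5 is not defined well enough to fix its error rate or power

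*Combined protocol and SAP*

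**What the plan says.** **Endpoint.** Section 2.1.3 defines it as "Quantitative measurement of ingesta (caloric and protein intake), monthly between M-1" and M6, and the summary has the same definition. Neither names a contrast. The schedule in 5.2 sets the collection as "3 consecutive days, for lunch and dinner, at a time t between M-1 and M0, then monthly". It shows no intake collection in the inclusion column, so the inclusion value must be the M-1 to M0 round.

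**Test.** Section 6.2.1: "The evolution of caloric and protein intakes between inclusion and 6 months will be compared between the 2 groups by a Wilcoxon Mann-Whitney test". Section 6.2.5 names the same inclusion-to-6-month comparison as the main criterion. Section 6.2.3 sets the level at 5%.

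**Allocation.** Section 3.3: "Randomization will be stratified by center (seniors's residents) and performed in a 1:1 ratio". The test names no home.

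**Intermediate rounds.** For M1 to M5, 6.2.1 offers only a graph, under its secondary endpoints: "The evolution of all the parameters collected throughout the monitoring will be described graphically".

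**Missing data.** Section 6.2.7 analyzes every included resident. Under 5.3.1, residents who no longer wish to take part "will be removed from the study as soon as this request is made". Section 6.2.5 replaces a missing primary value by the worst value and then by the mean of the group. It says nothing more about the rule.

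**Size.** Section 4.1 expects about 60 eligible residents. Section 6.2.2 reports no calculation and no data on which to base one.

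**The concern.** There are two separate issues.

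1. **Precision.** A two-group rank test on the change subtracts baseline but does not adjust for it. Unless intakes at the two rounds are almost perfectly correlated, subtraction leaves more variance than adjustment does. With about 60 residents that matters, and both baseline intake and home are already recorded.

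2. **Missing M6 values.** They can be expected in this population, and every included resident must be analyzed, so the imputation rule will shape the result. The two rules pull in different directions: the group average makes the data look more informative than they are, and the worst value dilutes a real effect. Because 6.2.5 leaves the rule open, two analysts following the plan could report different p-values, and neither could say which is the primary one.

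**Working it through.** **Plan's own figure.** There is none to reproduce; 6.2.2 states that no calculation was made.

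**Inputs from the documents.** About 60 residents (4.1) and 1:1 allocation (3.3), so about 30 per arm; 6 homes (4.1); 5% level (6.2.3; sidedness not stated, two-sided assumed); rounds and meals from 2.1.3 and 5.2.

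**Inputs assumed.** Effect d = 0.5 SD of a single-round intake, constant over M1 to M6; equal correlation ρ = 0.5 or 0.7 between rounds; normal data; no home effect; M6 missing at random in 10, 20 or 30%.

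**Step 1: data used.** 1 + 6 = 7 rounds; 7 × 3 days × 2 meals = 42 meals per resident. The test uses 2 rounds, 2 × 3 × 2 = 12 meals.

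**Step 2: precision with complete data.** In units of the single-round variance:
- change score: v = 2(1 − ρ)
- M6 adjusted for baseline: v = 1 − ρ²
- ratio: 2/(1 + ρ), which is 1.33 at ρ = 0.5 and 1.18 at ρ = 0.7

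Power ≈ Φ(√e × d/√(2v/30) − 1.96), with e = 3/π for the rank test (√e = 0.977) and e = 1 for the adjusted comparison.

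| ρ | Analysis | v | d/√(2v/30) | after √e | Power, formula | Power, simulated |
|---|---|---|---|---|---|---|
| 0.5 | planned test | 1.00 | 1.936 | 1.892 | 47% | 45% |
| 0.5 | M6 adjusted for baseline | 0.75 | 2.236 | 2.236 | 61% | 59% |
| 0.7 | planned test | 0.60 | 2.500 | 2.443 | 69% | 66% |
| 0.7 | M6 adjusted for baseline | 0.51 | 2.712 | 2.712 | 77% | 75% |

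In the simulation (6 homes of 10), adding home to the baseline-adjusted model leaves power at about 59% / 75%. This is expected, because the simulated data contain no home effect. The gain shown is therefore due to baseline.

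**Step 3: group-average imputation, no true effect.** Type I error of the Mann-Whitney test, simulated, rounded over both correlations:

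| M6 missing | M6 intake imputed, own baseline then subtracted | Change imputed |
|---|---|---|
| 10% | about 6% | about 9% |
| 20% | about 8% | about 17% |
| 30% | about 9% | about 30% |

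Under both readings the imputed residents borrow the same arm mean but count as independent observations. When the change is imputed they also share one identical value, so the spread shrinks as well.

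**Step 4: worst-value imputation, 0.5 SD effect, 20% missing.** Simulated power at ρ = 0.5 / 0.7:
- worst change observed in either arm: about 22% / 33%
- the resident's own lowest recorded intake: about 38% / 57%

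Type I error stays near 5% under both when missingness is equal between arms.

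**Step 5: what M1 to M5 add when M6 stays the target.** At 20% missing, a repeated-measures model with baseline and home has 49% / 67% power, against 46% / 63% for adjusted M6 in completers: 3 and 4 points. When low eaters leave more often, it is 54% / 68% against 48% / 64%: 6 and 4 points. Its null rejection rate at 20% random missingness was 4.3% / 6.0% (unstructured covariance, 2,000 runs).

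**The case against.** The strongest reply is that this is a pilot. Section 6.2.2 sets no power target, its purpose is preliminary data, and a rank test is a sound choice for a small sample whose meal consumption is partly graded in quarters (2.1.3). Much of this stands. The rank test is not invalid, and leaving out home costs precision at most. The simulations used normal data, which favours a linear model. But the plan still tests at 5%, and an open imputation rule damages preliminary estimates as well as p-values.

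A reader might also infer more than the documents support:
- **That five of seven rounds are wasted at great cost.** With M6 as the target, M1 to M5 add only about 3 to 6 points of power. Larger gains need a different target, the average over M1 to M6, and a roughly constant effect.
- **That the plan never states its contrast.** Sections 2.1.3 and the summary omit it, but 6.2.1 and 6.2.5 agree on it. Section 2.2.2 speaks of "the resident follow-up period (M0 to M6) depending on the randomization arm", but under the secondary-endpoint heading, so it creates no clear conflict.
- **That imputation certainly ignores the resident's own M1 to M5 intakes.** The group average does. The worst value does not if it means the resident's own lowest intake, and 6.2.5 does not exclude that.
- **That the type I error is 17% or 30%.** This holds only if the change is imputed. If the M6 intake is imputed, the inflation is moderate.
- **That adjusting for home brings a known gain.** The size of any home effect is unknown.

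**Conclusion.** The point holds in two parts. The textual omissions are certain: no baseline covariate, no stratifying home, and an imputation rule that leaves open whose worst value is used, what quantity is imputed and which result is primary.

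The sizes are conditional on the assumed inputs. With complete data the cost is precision only, about 14 points of power at correlation 0.5 (45% to 59%) and 9 at 0.7 (66% to 75%). With 20% of M6 missing, wording alone moves the type I error of group-average imputation between about 8% and about 17%, and the power under worst-value imputation between about 22% and 38% (correlation 0.5) or 33% and 57% (correlation 0.7). Every reading of the group-average rule exceeds the stated 5%. The imputation rule is the more pressing of the two; the missing contrast in 2.1.3 and the summary is editorial.

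**What to change.** **Section 6.2.1.** Keep M6 as the primary contrast. Estimate the arm difference in M6 intake adjusted for baseline intake and home, separately for calories and protein. A repeated-measures model of M1 to M6 with the same covariates is a suitable way to use the data of residents who miss M6; if it is chosen, pre-specify the covariance structure, a fallback and small-sample degrees of freedom. Keep the Mann-Whitney test on observed changes as a sensitivity analysis.

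**Section 6.2.5.** Base no p-value on group-average imputation. Keep worst-value imputation as a sensitivity analysis, stating whose worst value it is and whether the intake or the change is imputed. Say which analysis is primary and how deaths before M6 are handled.

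**Editorial.** Repeat the inclusion-to-M6 contrast in 2.1.3 and the summary, and say that the inclusion value is the M-1 to M0 round.

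**Cost.** Wording and a standard model; no new data. The downside is more modelling assumptions with about 60 residents, and, for residents without M6, a missing-at-random assumption that deaths or acute illness may break. The rank test and the worst-value analysis, kept as sensitivity analyses, show how far the result depends on these assumptions.
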